4.1.6. Management of other dates

The rules for substitution of missing or incomplete death date are as follows:

Table (4.1.6) 1 - Substitution rules of death date

Date to substitute		Substituted date
Death date	../mmm/yyyy	Last available date* if same month and year Otherwise: 01/mmm/yyyy
	../.../yyyy	Last available date* if same year Otherwise: 01/JAN/yyyy
	../.../....	No substitution

Notes:

../mmm/yyyy = missing day.

../.../yyyy = missing day and month.

../.../.... = totally missing date.

- * Last available date is defined as maximum date among completed dates relative to patient's information otherwise.

If no specific management of dates is defined, missing information is substituted as defined below:

Table (4.1.6) 2 - Substitution rules of dates if no specific management is defined

Date to substitute	Substituted date
../mmm/yyyy	01/mmm/yyyy
../.../yyyy	01/JAN/yyyy
../.../....	No substitution

Notes:

../mmm/yyyy = missing day.

../.../yyyy = missing day and month.

../.../.... = missing date.

For assessments with time also collected and useful for the analysis, substitution rules are as follows:

Table (4.1.6) 3 - Substitution rules of dates and times if no specific management is defined

Date and time to substitute	Substituted date and time
dd/mmm/yyyy hh-...	dd/mmm/yyyy hh:00
dd/mmm/yyyy ...-...	dd/mmm/yyyy 00:00
../mmm/yyyy ...-...	01/mmm/yyyy 00:00
../.../yyyy ...-...	01/JAN/yyyy 00:00
../.../.... ...-...	No substitution

Notes:

hh-... = missing minutes.

...-... = missing time.

../mmm/yyyy = missing day.

../.../yyyy = missing day and month.

../.../.... = missing date.

(as seconds are not collected in the electronic case report form (e-CRF) they will always be substituted by 00).

4.2. Specific analytic definitions and data handling conventions

4.2.1. Study patients: Disposition, baseline characteristics and follow-up

4.2.1.1. Disposition of patients

All withdrawal reasons occurred in the study will be taken into account.

4.2.1.2. Protocol deviations

For the description of protocol deviations, the 6 following categories are considered in accordance with ICH E3 guideline and ICH E3 Q&A:

- Selection/inclusion criteria not fulfilled.
- Patient having withdrawal criteria but not withdrawn.
- Incorrect treatment or dose received.
- Forbidden concomitant treatment.
- Endpoint assessment possibly affected.
- Safety possibly affected.

4.2.1.3. Demographic data and other baseline characteristics

4.2.1.3.1. Demographic data

Age (years) is calculated in the ClinTrial database as:

$$(\text{Date of inclusion} - \text{Date of birth})/365.25.$$

The result is truncated and not rounded. If the day and/or month of inclusion date and/or birth date is/are missing, the calculation is done by using the year.

4.2.1.3.2. History of AML

Disease duration

Disease duration (years) is calculated as:

$$(\text{Inclusion visit date} - \text{Date of the first diagnosis})/365.25.$$

Treatment free interval

Treatment-free interval since previous AML treatment line (days) and Treatment-free interval since previous MDS treatment line (days) are defined as:

$$(\text{Date of first IMP intake} - \text{Date of end of the last prior drug therapy}).$$

Of note, in case of partial or incomplete dates:

S 64315

CL1-64315-004 – Statistical Analysis Plan – Final V1.0

Missing diagnosis date		Substituted diagnosis date
../mm/yyyy	⇒	Diagnosis date=01/mm/yyyy
../.../yyyy	⇒	Diagnosis date=01/01/yyyy
Missing end date of the last prior therapy		Substituted end date of the last prior therapy
../mm/yyyy	⇒	End date of the last prior therapy=start date of the last prior therapy + 1 day if same month and year otherwise: End date of the last prior therapy =01/mm/yyyy
../.../yyyy	⇒	End date of the last prior therapy=start date of the last prior therapy + 1 day if same year otherwise: End date of the last prior therapy=01/01/yyyy
../.../...	⇒	End date of the last prior therapy=start date of the last prior therapy + 1 day

Notes:

If start date of the last prior therapy is partially or completely missing, follow the substitution rules if no specific management is defined (Table (4.1.6) 2 - Table (4.1.6) 3).

../mm/yyyy = missing day.

../.../yyyy = missing day and month.

4.2.1.3.3. Medical history and surgical or medical procedures history other than AML

The existence of a history (Yes/No) is defined from the presence, or not, of a primary SOC and/or PT, persistent or not at the time of study entry.

4.2.1.3.4. Signs and symptoms related to AML or prior therapies received for studied disease

The existence of a sign or symptom (Yes/No) is defined from the presence, or not, of a primary SOC and/or PT.

4.2.1.3.5. Previous therapies for AML

Of note, for patients entering the study with an AML secondary to MDS, previous therapies will be reported concerning AML treatment only.

The ATC classification (ATC code = 5 digits) is composed of 4 levels:

- The first (1 digit) represents the anatomico-physiological class.
- The second (2 digits) represents the pharmacological class.
- The third (1 digit) represents the pharmacological sub-class.
- The last (1 digit) represents the therapeutic class.

Previous treatment is defined as any treatment recorded in the eCRF page “Previous drug treatments for acute myeloid leukaemia (AML) or for previous myelodysplastic syndrome (MDS)”.

The existence of a previous radiotherapy (Yes/No) is defined from the presence or not of a verbatim for the previous radiotherapy involved site at inclusion visit.

The existence of a previous drug treatment (Yes/No) is defined from the presence, or not of an “ATC classification” and/or a “preferred name” for the previous drug treatment at inclusion visit.

The existence of a previous transplant (Yes/No) is defined from the presence, or not of previous transplant date at inclusion date.

The existence of a previous surgery (Yes/No) is defined from the presence or not of a verbatim for the previous surgery at inclusion visit.

The number of treatment lines is calculated as the sum of all previous treatment lines received, since diagnosis date of the studied disease (regardless the type of therapy).

The number of relapses is calculated as the sum of all previous lines with CR (including CR MRD-, CR, CRi and Haematologic relapse responses) as best response received, since diagnosis date of the studied disease (regardless the type of therapy).

The specific treatment lines described with the corresponding code lists are the following:

- 3427.1 Cytarabine 20221(WHODDB3).
- 3601.2 Treatments containing fludarabine 20221 (WHODDB3).
- 3428.2 Anthracyclines and related substances 20221(WHODDB3).
- 4273.0 Hypomethylating agents (HMAs) for CL164315004 study 20221 (WHODDB3).
- 3430.1 Azacitidine 20221(WHODDB3).
- 3422.1 Decitabine 20221(WHODDB3).
- 3429.1 Lenalidomide 20221(WHODDB3).
- 3594.2 Investigational drugs 20221(WHODDB3).
- Stem cell transplant and bone marrow transplant (no code list associated – To refer to previous transplant section allograft or autograft)
- 1869.0 Systemic and local treatment containing glucocorticoids DDB320221.
- 1728.2 Treatments containing an alkylating agent DDB320221.
- 3600.2 Treatments containing cyclophosphamide 20221(WHODDB3).
- 3602.0 Treatments containing antimetabolites agents DDB320221.
- 3609.0 Treatments containing protein and tyrosine kinase inhibitors DDB320221.
- 3605.1 Treatments containing etoposide 20221(WHODDB3).
- 3914.0 Granulocyte colony stimulating factor 20221(WHODDB3).
- 4131.1 Treatments containing enasidenib 20221(WHODDB3).
- Gemtuzumab ozogamicin (Mylotarg®) (drug code: 15959801001, version WHODDB32022.1)
- Ivosidenib (Tibsovo®) (drug code : 09165501001, version WHODDB32022.1)

No substitution of missing or incomplete previous drug treatments are applied.

4.2.1.3.6. Initial disease assessment

PB blasts in blood expressed in SI unit (G/L) in “blood haematology” form will be converted to % unit by dividing by the corresponding WBC value.

Information concerning platelets transfusion-independence prior to LID1 and red blood cells transfusion-independence prior to LID1 (i.e. before the first IMP intake) will be retrieved from the “History of the Acute Myeloid Leukaemia” e-CRF form. The patients having received a transfusion prior to LiD1 will be considered as transfusion-dependent.

4.2.1.4. TLS prevention

TLS prevention treatment lines (anti-hyperuricemic therapy) are referenced in the code list n°3399.0 WHOODB3 20221.

4.2.1.5. Extent of exposure and treatment compliance

Global treatment duration

Global treatment duration (weeks) is defined as $(\min [\max (\text{last intake date of the last cycle azacitidine} + 21 \text{ days, last intake date of S64315} + 6 \text{ days), death date, withdrawal date}] - \text{first IMP intake} + 1) / 7$.

Treatment duration for S64315 including LID period (QW)

Treatment duration (days) for S64315 is defined as $[(\min (\text{last infusion date} + 6 \text{ days, death date, withdrawal date}) - \text{first S64315 infusion date}) + 1]$.

Treatment duration (weeks) for S64315 is defined as $[(\min (\text{last infusion date} + 6 \text{ days, death date, withdrawal date}) - \text{first S64315 infusion date}) + 1] / 7$.

Treatment duration for S64315 excluding LID period (QW)

Treatment duration (days) for S64315 is defined as $[(\min (\text{last infusion date} + 6 \text{ days, death date, withdrawal date}) - \text{first S64315 infusion date of cycle 1}) + 1]$.

Treatment duration (weeks) for S64315 is defined as $[(\min (\text{last infusion date} + 6 \text{ days, death date, withdrawal date}) - \text{first S64315 infusion date of cycle 1}) + 1] / 7$.

Treatment duration for azacitidine

Treatment duration (days) for azacitidine is defined as $[\min (\text{last intake date of the last cycle} + 21 \text{ days, death date, withdrawal date}) - \text{first azacitidine intake} + 1]$.

Treatment duration (weeks) for azacitidine is defined as $[\min (\text{last intake date of the last cycle} + 21 \text{ days, death date, withdrawal date}) - \text{first azacitidine intake} + 1] / 7$.

S64315 treatment duration in LID period:

S64315 treatment duration in LID period LID(days) is defined as $[\min (\text{first S64315 infusion date of cycle 1-1, death date, withdrawal date}) - \text{first S64315 infusion date of LID1}] + 1$.

Note: In case of missing first S64315 at cycle 1, S64315 treatment duration in LID period is defined as $[\min (\text{last S64315 infusion date in LID} + 6, \text{ death date, withdrawal date}) - \text{first S64315 infusion date of LID}] + 1$. LIDLID

LID period duration (weeks): LID period duration (days) / 7.

Cycle duration for S64315

Duration of cycle i (weeks) for S64315 is defined as $[\text{first IMP intake of cycle } (i+1) - \text{first IMP intake of cycle } i] / 7$.

Note: The duration of the last cycle for S64315 will be estimated to be 4 weeks for the calculation of dose intensity and relative dose intensity at the last cycle.

Cycle duration for azacitidine

Duration of cycle i (weeks) for azacitidine is defined as [first IMP intake of cycle $(i+1)$ – first IMP intake of cycle i] / 7.

Of note,

- The duration of the last cycle for azacitidine will be defined as [(last intake of last cycle + 21 days) – first intake of last cycle + 1] / 7.

Numbers of cycles for S64315/azacitidine

The number of cycles with study drug intake for S64315/azacitidine will be defined based on patient exposure data while on treatment excluding S64315 LID period. A patient is considered to enter in a cycle if there is at least one intake date.

Real administrated dose of S64315 will be recorded directly from S64315 infusion e-CRF page. For information, the administrated dose is recorded in mL within e-CRF. The conversion of the real administrated dose in mg is directly calculated by the data manager. Little variation between planned dose and real administrated dose can be expected due to feasibility (IMP preparation and injection).

Planned dose intensity (PDI) for S64315 (mg/week)

Planned dose intensity (PDI) for S64315 (mg/week)	Schedule (QW)
	4 intakes per cycle / 1 intake per LID week
Dose Level -1: 25 mg*	25 mg/ week*
Dose Level 1: 50 mg**	50 mg/ week**
Dose Level 2: 100 mg	100 mg/ week
Dose Level 3: 200 mg	200 mg/ week
Dose Level 4: 250 mg	250 mg/ week

* LID1 dose.

** LID2 dose

However, it is possible that intermediate or higher dose levels are added during the course of the study.

Cumulative dose for S64315

The cumulative dose (mg) for S64315 per patient in a time period (during the treatment period including LID or per cycle) is the sum of the total dose levels that the patient received within that period according to the compliance.

$$\text{Cumulative dose (mg)} = \sum_{\text{timeperiod}} (\text{Real Administrated dose (mg)}).$$

Dose intensity (DI) for S64315

The dose intensity (mg/ week) for S64315 per patient is defined as the cumulative dose (mg) received during the treatment period divided by the total treatment duration in weeks, including LID period.

$$DI \left(\frac{\text{mg}}{\text{wk}} \right) \text{ per patient} = \frac{\text{Cumulative dose (mg)}}{\text{Treatment duration (weeks)}}$$

The dose intensity (*mg/ week*) for S64315 per cycle is defined as the cumulative dose (mg) received during the cycle divided by the cycle duration in weeks.

$$DI \left(\frac{mg}{wk} \right) \text{ at cycle } i = \frac{\text{Cumulative dose (mg) received at cycle } i}{\text{Duration of cycle } i \text{ (weeks)}}.$$

The duration of the last cycle will be estimated to be (*) weeks.

(*): 4 weeks for regimen QW, 2 week for LID.

Relative dose intensity (RDI) for S64315

The RDI (%) for S64315 per patient measures the percentage of the total trial dose planned that was really administered. It is defined as the ratio of the dose intensity (mg/week) to the initial planned dose intensity (mg/week)

$$RDI \text{ (%) per patient} = \frac{DI \text{ (mg/wk)}}{\text{Planned dose intensity (mg/wk)}} * 100.$$

The RDI (%) for S64315 per cycle is defined as the ratio of the dose intensity (mg/week) at cycle *i* (including LID cycles) to the planned dose intensity (mg/week).

$$RDI \text{ (%) at cycle } i = \frac{DI \text{ at cycle } i \text{ (mg/wk)}}{\text{Planned dose intensity at cycle } i \text{ (mg/wk)}} * 100.$$

Treatment interrupted for S64315

A treatment interruption is defined according to the S64315 infusion e-CRF page (Did the patient receive the IMP infusion (Yes/No)).

Number of cycles with at least one treatment interruption for S64315 experienced by a patient over the treatment period will be calculated.

Cycle delay for S64315

A cycle delay is defined according to the S64315 infusion e-CRF page (infusion postponed (Yes/No) at D2 of the cycle *i* or of LID2). Moreover, a delay of LID2 will be also considered if the duration of the LID1 is higher than 7 days, while a delay of cycle *i* will be also considered if the duration of the cycle *i-1* is higher than (*). In case of missing cycle delay reason, reason of cycle delay will be considered as unknown. The delay in days will be derived, based on the dates of administration.

Delay (days) of cycle *i* = (first IMP intake of cycle *i*) – (first IMP intake of cycle *i-1* + *x* days).

(*): 30 days for regimen QW (theoretical cycle duration + 2 days for potential technical or logistical difficulty). In the delay duration formulae above *x*=30.

(*) *x*=16 days if Cycle *i-1* is the LID period.

Number of cycles delayed for S64315 experienced by a patient over the treatment period will be calculated among patients experiencing a cycle delay.

Dose modification for S64315

A dose modification is defined according to the S64315 infusion e-CRF page (Has the dose been modified since the last infusion (Yes/No), with a dose level different from the dose level at previous infusion).

Number of dose modifications for S64315 experienced by a patient over the treatment period will be calculated among patients experiencing a dose modification.

Time to first dose modification for S64315 will be calculated among patients experiencing a dose modification from the first study drug intake until the first dose modification.

Partial dose administered for S64315

A partial dose administered is defined according to the S64315 infusion e-CRF page (Was full dose administered ? (Yes/No))

Number of cycles with partial dose experienced by a patient over the treatment period will be calculated among patients.

Number of days dosed for azacitidine

The number of days dosed for azacitidine is defined as the total number of days with azacitidine intake (overall and by cycle).

Average number of days dosed per cycle for azacitidine

The average number of days dosed per cycle for azacitidine is defined as the total number of days dosed for azacitidine divided by the number of cycles according to the period of interest (i.e. for overall period: number total of cycles / for each cycle: 1):

$$\text{Average days dosed per cycle} = \frac{\text{Total number of days dosed}}{\text{Number of cycles}}$$

Number of days dosed with planned dose level for azacitidine

The number of days dosed with planned dose level for azacitidine is defined as the total number of days with azacitidine intake corresponding to the planned dose level of 75 mg/m² (the actual dose administered is equal to 75mg/m² or within the interval 75 ±7.5 mg/m²).

Average number of days dosed per cycle with planned dose level for azacitidine

The average number of days dosed with planned dose level for azacitidine per cycle is defined as the total number of days dosed with planned dose level for azacitidine divided by the number of cycles according to the period of interest (i.e. for overall period: number total of cycles / for each cycle: 1):

$$\text{Average days dosed with planned dose level per cycle} = \frac{\text{Total number of days dosed with planned dose level}}{\text{Number of cycles}}$$

Real administrated dose of azacitidine will be recorded directly from azacitidine injection e-CRF page (Administered dose (mg)).

Planned dose intensity (PDI) for azacitidine:

Planned dose intensity (day): 75 mg/m²/day (fixed).

Planned dose intensity (cycle or overall): (75 mg/m²/day (fixed) * 7) / 28.

Cumulative dose for azacitidine

The cumulative dose (mg/m²) for azacitidine per patient during a time period (during the treatment period or per cycle) is the sum of the total dose levels that the patient received between the first and last treatment intake according to the compliance.

$$\text{Cumulative dose (mg/m}^2\text{)} = \sum_{\text{timeperiod}} \left(\frac{\text{Real Administrated dose (mg)}}{\text{BSA (m}^2\text{)}} \right).$$

Dose intensity (DI) for azacitidine

The dose intensity (mg/m²/day) for azacitidine per patient is defined as the cumulative dose (mg/m²) received during the treatment period divided by the overall treatment duration of azacitidine.

$$DI \left(\frac{\text{mg/m}^2}{\text{day}} \right) \text{ per patient} = \frac{\text{Cumulative dose (mg/m}^2\text{)}}{\text{Overall treatment duration of azacitidine}}.$$

The dose intensity (mg/day) for azacitidine per cycle is defined as the cumulative dose (mg) received during the cycle divided by the cycle duration of azacitidine.

$$DI \left(\frac{\text{mg/m}^2}{\text{day}} \right) \text{ at cycle } i = \frac{\text{Cumulative dose (mg/m}^2\text{) received at cycle } i}{\text{Cycle } i \text{ duration of azacitidine}}.$$

Relative dose intensity (RDI) for azacitidine

The relative dose intensity (%) for azacitidine per patient measures the percentage of the total trial dose planned that was really administered. It is defined as the ratio of the dose intensity (mg/m²/day) to the initial planned dose intensity (mg/m²/day).

$$RDI (\%) \text{ per patient} = \frac{DI (\text{mg/m}^2/\text{day})}{\text{Planned dose intensity (mg/m}^2/\text{day)}} * 100.$$

The relative dose intensity (%) for azacitidine per cycle is defined as the ratio of the dose intensity (mg/m²/day) at cycle *i* to the planned dose intensity (mg/m²/day).

$$RDI (\%) \text{ at cycle } i = \frac{DI \text{ at cycle } i (\text{mg/m}^2/\text{day})}{\text{Planned dose intensity at cycle } i (\text{mg/m}^2/\text{day)}} * 100.$$

Treatment interruption for azacitidine

A treatment interruption is defined according to the azacitidine injection e-CRF page (Did the patient receive at least one azacitidine injection (Yes/No)).

Number of cycles with at least one treatment interruption for azacitidine experienced by a patient over the treatment period will be calculated.

Number of azacitidine interruption days experienced by a patient over the treatment period will be calculated among patients experiencing a treatment interruption.

The number of azacitidine interruption days is the number of days on which azacitidine was scheduled to be administered but was not actually administered.

Cycle delay for azacitidine

A cycle delay is defined according to the azacitidine injection e-CRF page (Was the injection day postponed (Yes/No) at D1 of the cycle). Moreover, a cycle delay of cycle *i* will be also considered if the duration of the cycle *i-1* is higher than (*). In case of missing cycle delay

reason, reason of cycle delay will be considered as unknown. The delay in days will be derived, based on the dates of administration.

For $i > 1$, Delay (days) of cycle $i = (\text{first IMP intake of cycle } i) - (\text{first IMP intake of cycle } i-1 + x \text{ days})$

(*): 30 days for regular cycle (theoretical cycle duration + 2 days for potential technical or logistical difficulty). In the delay duration formulae above $x=30$.

Number of cycles delayed for azacitidine experienced by a patient over the treatment period will be calculated among patients experiencing a cycle delay.

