3.2.5. Treatments of patients

3.2.5.1. Extent of treatment exposure and treatment compliance

Details concerning definition on extent of exposure, treatment compliance are provided in [Appendix 4.2.1.5](#).

For S64315 and azacitidine separately the frequency distribution (n, %) or descriptive summary statistics (n, mean, SD, median, min, max, median, Q1, Q3) as applicable will be provided in

patients of the SS by planned dose level combination and overall for variables measured on a nominal scale according to the following classes:

- Extent of exposure*:
 - The global treatment duration (combined measure for S64315/azacitidine): summary statistics.
 - Treatment duration (weeks) overall and by treatment period (LID/Combination treatment).
 - Treatment duration (weeks) during combination treatment period (i.e., excluding LID) (< 4 weeks, [4-12[weeks, [12-24[weeks, [24-36[weeks, [36-48] weeks, >48 weeks).
 - LID duration ([0-1] week, [1-2] weeks and > 2 weeks).
 - Number of cycles (1 cycle, 2 cycles, 3-6 cycles, 7-10 cycles, > 10 cycles) during the combined treatment period.
 - Number of patients by cycle (LID, Cycle 1, Cycle 2, etc).
- Treatment compliance*:
 - Cumulative dose (mg) for S64315/ Cumulative dose (mg/m²) for azacitidine overall, by cycle (including LID), and for combination treatment.
 - Dose intensity (DI) (mg/week) for S64315/ DI (mg/m²/day) for azacitidine overall, by cycle (including LID), and for combination treatment.
 - Relative Dose Intensity (RDI) (%) for S64315/azacitidine overall, by cycle (including LID), and for combination treatment.
 - RDI for S64315(< 35%, [35-65[%, [65-100[%, ≥ 100%) overall, by cycle, and per treatment period (LID/Combination treatment).
 - RDI for azacitidine (< 62%, [62-85[%, [85-100[%, ≥ 100%) overall, by cycle, and per treatment period (Combination treatment).
 - Treatment interruption (Yes/No) during treatment period (including LID).
 - Reason of treatment interruption (Medical reason, Non-medical reason, Missing).
 - LIDLIDNumber of cycles with at least one treatment interruption for S64315 during treatment period (including LID).
 - Number of cycles with at least one treatment interruption for azacitidine during treatment period.
 - Cycle delayed (Yes/No) during treatment period (including LID).
 - Reason for cycle delayed (Medical reason, Non-medical reason, Missing).
 - Number of cycles delayed during treatment period (including LID).

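### SAP 4.2.1.5 defines azacitidine cycle duration only in weeks but compares per-cycle dose intensity with a per-day plan; applied as written, per-cycle DI and RDI are 7 times too high

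*SAP*

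**What the plan says.** All the definitions are in SAP 4.2.1.5 (Extent of exposure and treatment compliance).

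- **Cycle duration.** The length of cycle i is stated in weeks ("weeks) for azacitidine is defined as [first IMP intake of cycle"): the gap between the first intakes of successive cycles, divided by 7. The last cycle has its own rule, "The duration of the last cycle for azacitidine will be defined as [(last intake of last cycle + 21 days", less the first intake, plus 1, again divided by 7. No azacitidine cycle duration in days is given.
- **Per-cycle DI.** This quantity, given in mg/day, "is defined as the cumulative dose (mg) received during the cycle divided by the cycle duration of azacitidine". The displayed formula beneath that sentence carries the label mg/m²/day, and its denominator has no unit.
- **Plan.** "Planned dose intensity (cycle or overall): (75 mg/m²/day (fixed) * 7) / 28", which works out at 18.75 mg/m²/day.
- **Per-cycle RDI.** It "is defined as the ratio of the dose intensity (mg/m²/day) at cycle *i* to the planned dose intensity (mg/m²/day"), times 100.

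SAP 3.2.5.1 calls for DI in mg/m²/day by cycle and for "RDI for azacitidine (< 62%, [62-85[%, [85-100[%, ≥ 100%) overall, by cycle".

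Two neighbouring definitions in 4.2.1.5 are useful for contrast. S64315 uses weeks throughout: cycle duration in weeks, DI in mg/week, plan in mg/week. The overall azacitidine treatment duration is given in both days and weeks.

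**The concern.** The only denominator that the SAP supplies for the per-cycle DI makes it a dose per week, while the label and the planned value are per day. No conversion factor appears between them. A programmer who takes the defined duration and inserts it in the formula divides a weekly rate by a daily one.

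Dose intensity is among the endpoints listed for the primary objective in SAP 1.2, and RDI is to be tabulated by cycle in four classes. Those classes make sense only on the day scale. In a 28-day cycle at full dose, 4, 5, 6 and 7 injections give 57%, 71%, 86% and 100%, one in each class. On the scale as written, all four fall in the top class. The table would then not separate a cycle with 5 of 7 injections, the minimum azacitidine exposure for DLT evaluability in SAP Table (2.1) 1, from a complete one.

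**Working it through.** **Inputs**

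- Planned schedule: 75 mg/m² daily for 7 days of a 28-day cycle (SAP 1.3.1), so 75 × 7 = 525 mg/m² per cycle.
- Planned dose intensity per cycle: 525 / 28 = 18.75 mg/m²/day (SAP 4.2.1.5).
- Cycle duration: L / 7 weeks, where L is the cycle length in days (SAP 4.2.1.5).

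**Step 1: which unit reproduces the plan.** A complete 28-day cycle with the duration in days gives 525 / 28 = 18.75, and 18.75 / 18.75 = 100%. With the duration in weeks it gives 525 / 4 = 131.25, and 131.25 / 18.75 = 700%. Only days return 100% for full compliance.

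**Step 2: general form.** For k full-dose injections in a cycle of L days:

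- as written: RDI = [75k / (L/7)] / 18.75 = 28k / L
- in days: RDI = [75k / L] / 18.75 = 4k / L

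The ratio is 7 for every k and L.

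**Step 3: non-last cycles, full dose**

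| Cycle length (days) | Injections | RDI as written | RDI in days |
|---|---|---|---|
| 28 | 7 | 700% | 100% |
| 28 | 5 | 500% | 71.4% |
| 28 | 3 | 300% | 42.9% |
| 28 | 1 | 100% | 14.3% |
| 35 | 7 | 560% | 80.0% |
| 35 | 1 | 80% | 11.4% |
| 56 | 1 | 50% | 7.1% |

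**Step 4: last cycle.** With injections on D1 to D7 the length is 6 + 21 + 1 = 28 days, and the result is again 700% against 100%. With D1 only, the length is 0 + 21 + 1 = 22 days. As written, 75 / (22/7) / 18.75 = 127.3%; in days, 75 / 22 / 18.75 = 18.2%.

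**Step 5: reduced dose.** One half-dose injection in a 28-day cycle gives, as written, 37.5 / 4 / 18.75 = 50%.

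**Step 6: does the other planned value rescue the formula?** The SAP also lists a plan of 75 mg/m²/day for a single day. Against that, a complete 28-day cycle would score 131.25 / 75 = 175% and a single injection 18.75 / 75 = 25%, so it does not.

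**The case against.** The best defence is the label. The azacitidine DI is marked mg/m²/day in SAP 3.2.5.1 and in the displayed formula, and the RDI text repeats that unit for both numerator and plan. Unlike the S64315 formula, the azacitidine denominator does not say weeks. A programmer who works from the output unit would convert to days and get the right answer. A value near 700% for a fully dosed patient would also be conspicuous, and SAP section 1 plans a statistical data review before database lock, although it does not say which outputs are reviewed.

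This shows what was intended, but it leaves the text inconsistent: the label contradicts the only cycle duration that is defined. A table showing classes alone would read ≥ 100% and raise no alarm.

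Other parts of the defence stand in full. A reader might infer that every cycle with at least one injection falls in the top class, so that under-dosing cannot be seen at all. The documents do not support that. A single injection in a longer cycle scores below 100% (80% at 35 days), and Protocol Table (8.12) 2 provides for both delayed cycles and reduced azacitidine doses. Under-dosing is also reported through cumulative dose by cycle, days dosed, interruption days, interruptions and cycle delays (SAP 3.2.5.1). Nor does the error carry over to overall RDI with the same certainty: a treatment duration in days exists, and the mg/m²/day label largely settles which one to use.

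**Conclusion.** The inconsistency is real and should be corrected. If the defined duration is used without conversion, per-cycle azacitidine DI and RDI are inflated by exactly 7, whatever the cycle length or number of injections. The specific percentages depend on conditions: 700%, 500% and 100% for seven, five and one injections hold at full dose in a non-last cycle of exactly 28 days. Under those conditions every cycle with any injection falls in the ≥ 100% class. More generally most under-dosed cycles do, but not all.

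The certain error stops at per-cycle azacitidine DI and RDI. Because dose intensity sits under the primary objective, a reader might infer that the dose-finding result is at risk. It is not: DLT evaluability rests on counts of doses (SAP 2.1), not on RDI, so DLT counts and the MTD are untouched. The SAP also records that escalation has stopped and that the expansion part will not be conducted (1.3 and 1.3.1). What is at stake is the accuracy of a descriptive exposure table in the abbreviated report.

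**What to change.** In SAP 4.2.1.5:

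1. For DI and RDI, define azacitidine cycle duration in days, using the same date differences without the division by 7, for both non-last and last cycles.
2. State that the overall azacitidine DI uses the treatment duration in days.
3. In the per-cycle DI sentence, change mg/day to mg/m²/day and mg to mg/m².

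Moving the plan to 131.25 mg/m²/week (18.75 × 7) would also restore consistency, but the mg/m²/day labels in 3.2.5.1 and 4.2.1.5 would then have to change as well, so the definition in days is the simpler route.

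The cost is a few words in the SAP and a check of the derivation program. A complete 28-day cycle must return 100% and five of seven injections 71.4%. No data collection changes and no clinical rule is touched.
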